11.0 HUMAN SUBJECTS

This study will be conducted in compliance with the protocol, ICH Good Clinical Practice (GCP) guidelines, and 45 CFR Part 46.

11.1 Participants' Confidentiality

All laboratory specimens, questionnaires, evaluation forms, reports, transcripts, and other records will be identified by SID and participant initials only, to maintain participant confidentiality. All paper records with personally-identifying information will be kept in a locked file cabinet in a limited secure access area at each study site. All computer entry and networking programs will be done with coded numbers only. Clinical information will not be released without written permission of the participant, except as necessary for monitoring by the protocol team or NICHD. Every effort will be made to ensure that study participants are protected from risks.

Breach of Confidentiality: A potential risk to participants is violation of confidentiality. We will take the utmost caution to protect the confidentiality of all responses. We will minimize this risk by maintaining confidentiality and discretion throughout all research procedures and data management and analysis.

Participants may be concerned about the security of their data, particularly since it is collected and stored electronically. UNC and Duke have significant experience developing security protocols for

Internet-based studies, and we will take a variety of steps to ensure participant security, including using a dedicated server behind a firewall, encryption of data, separation of identifiers from responses, and password-protected access to data. Therefore, we believe that this risk will be minimal.

For both Tough Talks intervention arms, participants will create a unique username that does not contain any identifying information but will be their username on the app. Participants will not be able to privately communicate with each other on the app. Trained research staff at the University of North Carolina will monitor the website daily to ensure violations to privacy.

11.2 Certificate of Confidentiality

This research specifically targets a vulnerable population, children – YMSM ages 15-17. We will take every available step to minimize the risk of identifying/linking data being subpoenaed, stolen, or inadvertently released. First, the Tough Talks has secured a Certificate of Confidentiality from the NIH. Second, all research staff members are required to complete ethical clearance certification regarding protection of human subjects through their relevant IRBs. Third, all studies will have documented procedures to safeguard against the risk of the linking information being stolen by keeping such information in locked spaces to which only essential study personnel who have completed CITI certification for human subjects research ethics training (<http://citiprogram.org>) will have access. Per Section 2012 of the [21st Century Cures Act](#) as implemented in the [2017 NIH Certificates of Confidentiality Policy](#), all ongoing or new research funded by NIH as of December 13, 2016 that is collecting or using identifiable, sensitive information is automatically issued a CoC. As noted on the NIH website (<http://grants.nih.gov/grants/policy/COC/faqs.htm#187>), a Certificate of Confidentiality will help the research team "...avoid compelled 'involuntary disclosure' (e.g., subpoenas) of names and other identifying information about any individual who participates as a research subject (i.e., about whom the investigator maintains identifying information) during any time the Certificate is in effect."

11.3 Risks and Benefits

11.3.1 Risks

To minimize the risk of participants feeling uncomfortable about answering personal questions, we will use Computer Assisted Self Interview (CASI) methods for the study's assessments. In CASI, participants read assessment questions on a laptop computer or mobile phone and use a combination of mouse click and keyboard/touchscreen entry to input the answers themselves. Study staff may be available to assist participants with questions or technical difficulties on the CASI. Participants will also be able to refuse to answer any question that makes them uncomfortable. In-depth interviews will be conducted face-to-face or online.

To minimize risks to confidentiality, we will secure study data with all appropriate physical, electronic and operational protections. Data will be stored in a physically secure environment. All data files will have encryption and strong password protection. Any identifiable data will either be stored on UNC secure servers or will be on fully encrypted laptops. CASI assessments and online eligibility screening will take place on Qualtrics. Access to data will be on a role-based standard; only those study staff who require access to each type of data to complete their study-related roles will be allowed access. All study staff will be trained in security and confidentiality procedures, and will sign a confidentiality agreement before receiving access to any participant data.

We will also develop procedures to minimize indirect disclosure that a participant is participating in an HIV- related research study, or a study that enrolls MSM. For each mode of contact information, we will ask specifically whether anyone else potentially has access to that mode of communication, and if it is acceptable to leave a non-specific message about participation in a health study. No study-related messages will ever mention HIV prevention or the nature of the research study.

We use SSL encryption for transfers of information online, and Qualtrics has a business partner HIPAA agreement with UNC. Qualtrics is HIPAA compliant.

UNC will use Dedoose software to perform all qualitative analyses. Dedoose is a web-based application for organizing and analyzing textual, audio, and video data (qualitative) along with outstanding functionality for their integration with survey, test score, ratings, and demographic data (quantitative). Dedoose employs the highest levels of data encryption available for a web application in all data storage, back up, and transmission. Dedoose allows for project specific encryption feature.

In addition to a Certificate of Confidentiality, we will protect participants in the following ways (which correspond to the potential risks described in A.3):

- 1) Breach of confidentiality. We will take every precaution to minimize risks to study participants. All research staff members are required to complete ethical clearance certification regarding protection of human subjects through UNC-CH and Duke University or at their participating study site. We also have a strong data and safety monitoring plan in place to protect participants. Adverse events will be reported to the UNC-CH and Duke University and study site-specific IRBs using the Adverse Event Reporting Forms. Reports will be sent within 24 hours of notification by the PIs. Annual updates on enrollment and retention will also be sent to the IRBs.

All data collection will take place in secure and supervised clinical settings. All study personnel names on this protocol have completed training and received certification in Human Subjects Research Protection (CITI Program) and HIPAA regulations. They will continue to renew this training in compliance with institutional policies. Participants will be asked to provide informed written consent to audio recording (usability testing, field testing) and HIV testing, and medical chart abstraction. To assure confidentiality and protection of the participants during audio recording, all files and transcripts will be stored on a password protected, encrypted computer in a locked file cabinet in a secured office. To additionally preserve confidentiality, we will only use participants' SIDs and names will not be used in data analysis. Informed consent forms, audio files, and transcripts will be kept in locked files and password-protected databases in a locked office accessible only to investigators. Audio files will be destroyed within one year of study completion.

- 2) Emotional discomfort during the assessment and/or while using the mobile app. While participants will be informed that they may refuse to answer any questions at any time, responses or reactions to certain questions may indicate distress on the part of the participants. If at any time during the study, a participant divulges that he is at risk for harm, including but not limited to being abused or experiencing violence, if harm is suspected or likely, or if the participant states he is suicidal/homicidal, measures will be taken to ensure his safety locally. Reporting will be made as appropriate to the situation and the legal statutes, and referrals will be provided for appropriate support, counseling or treatment resources.

- 3) Discomfort during collection of blood specimen. Whenever possible, we will conduct a medical chart review in order to minimize the need for blood sample collection for participants. There are only two time points in the study that require a potential blood draw if VL is not provided in the participants' medical chart (enrollment and 6-month assessment). All necessary blood sample draws will be executed by trained professionals within the SRV sites or independent laboratory.

In addition to a Certificate of Confidentiality, we will protect participants in the following ways:

We will take every precaution to minimize risks to study participants. Adverse events will be reported to the UNC-CH IRB, individual research PI institutional IRBs, and STUDY site-specific IRBs per each institution's IRB reporting requirements using Adverse Event CRF. When possible, reports will be sent within 24 hours of notification by the PIs. Annual updates on enrollment and retention will also be sent to the IRBs.

All data collection will take place in secure and supervised clinical settings. All study personnel have completed training and received certification in Human Subjects Research Protection (CITI Program) and HIPAA regulations. They will continue to renew this training in compliance with the UNC IRB policy as well as their individual institutional policies.

11.3.2 Benefits

The risk to individual participants is small and the potential benefit to both the individual and society is substantial. The main benefit of the proposed study to society is the development of a potentially feasible and acceptable mobile app that improves HIV disclosure. Participants may experience improvements in their own experiences disclosing their HIV status, thereby potentially reducing their risk for transmitting HIV and risks and costs to society. Therefore, the risk/benefit ratio is favorable. Study participants will be compensated for their time.

YMSM account for nearly two thirds of all new HIV infections in the US and YMSM are the only risk group experiencing a significant increase in HIV incidence. If successful, our intervention will improve these outcomes in our subject population. Given this high potential impact and low potential hazards to participants, we find that a clear examination of these research questions outweighs the previously mentioned risks. The effectiveness of a novel, scalable, technology driven, intervention to address HIV disclosure is understudied with this population. Given the significant health outcomes associated with HIV infections, and the paucity of intervention programs for this population of young adults, the knowledge to be gained from this research is significant. The risks to participants are reasonable in relation to the importance of the knowledge to be gained.

11.4 Institutional Review Board (IRB) Review and Informed Consent

This protocol, the informed assent/consent documents, and any subsequent modifications will be reviewed and approved by the UNC IRB who is responsible for the oversight of the study. The informed assent/consent will describe the purpose of the study, the procedures to be followed, and the risks and

benefits of participation. Consent/assent will be obtained to explain the nature, significance, and risks of the study. Sample informed consent/assent forms are included.

11.5 Waiver of the Requirement for Parental Permission for Special Circumstances

The site IRBs and the UNC IRB as the central IRB will be requested to grant a waiver of parental permission to participate in this research study for youth participants under (not inclusive of) the age of 18.

Under 45 CFR 46.408 (c), an IRB has the authority to waive parental permission if it determines that “a research protocol is designed for conditions or a subject population for which parental or guardian permission is not a reasonable requirement to protect the subjects” and “an appropriate mechanism for protecting the children who will participate as research subjects is substituted” and “that the waiver is not inconsistent with Federal, State, or local law.”

A request for a waiver of the requirement for parental permission is requested for 2 reasons: 1) many youth would be reluctant to participate in this study – which focuses on HIV and risks for poorer medication adherence – if they are required to get parental permission; and 2) many of the youth in our study are likely to be gay, bisexual, or have an attraction to persons of the same gender, but may not be out to their parents; requiring parental permission may place participants at risk for outing themselves as part of the LGBT community or having HIV. For these reasons, we believe it is important to be granted a waiver for parental permission for this study population.

11.6 Waiver of the Requirement for Signed Consent Form

11.6.1 For Eligibility Screening

An online consent process for the eligibility screening is proposed. The introduction to the screening interview includes all the required elements for consent (45 CFR 46.116). No identifying information on volunteers is recorded during the online screening until a participant is determined eligible (i.e., by marking “I do consent to be screened for eligibility”). Therefore, there will be no identifying link of who agreed to be screened or not screened for the study. In addition, the screening presents minimal risk to participants and involves no procedures that would require written consent outside of a research context. Under these conditions the IRB is authorized to modify the requirements to obtain a signed consent form for some or all subjects (45 CFR 46.117 [c]).

11.7 Prisoner Participation

NIMH has concluded that this protocol does NOT meet Federal requirements governing prisoner participation in human subjects research and should NOT be considered by local IRBs for the recruitment of prisoners. Subjects enrolled who subsequently become incarcerated or are placed in detention may not continue study participation. Study visits cannot be conducted during the period of incarceration or detention.

11.8 45 CFR Parts 160 and 164 Standards for Privacy of Individually Identifiable Health Information ("Privacy Rule" Pursuant to the Health Insurance Portability and Accountability Act - HIPAA)

Each site is responsible for adherence to their individual institution's HIPAA policies and procedures.

11.9 Study Discontinuation

This study may be discontinued at any time by the UNC IRB, NICHD, or other government agencies as part of their duties to ensure that research participants are protected.

12.0 PUBLICATION OF RESEARCH FINDINGS

Any presentation, abstract, or manuscript will be made available for review by the study sponsor(s) prior to submission.

Schedule of Events

Table 2: Schedule of Study Evaluations and Outcomes						
			BL	One-month	Three-months	Six-Months
Primary Outcomes						
Viral load suppression	Viral load suppression will be defined as HIV RNA < lower limit of detection as per the laboratory at each clinical site.	Medical Chart review or blood draw for study	X		X	X
Secondary Outcomes						
Condomless anal sex (CA) with potentially susceptible partner	≥1 act of CAI with a partner who is not known to be HIV-positive in the last 3 months.	CASI	X		X	X
Disclosure Self-Regulation (Behaviors)	Measure of desire and actual disclosure behaviors to family, peers and sex partners	CASI	X	X	X	X
Self-efficacy to disclose	Adapted version of disclosure self-efficacy measure for MSM (6 items) ¹⁴ .	CASI	X	X	X	X

Disclosure outcome expectations	Adapted version of disclosure outcome expectations measure for MSM (2 domains: self-evaluative expectancies - 6 items, and hedonistic outcome expectancies – 3 items) ¹⁴ .	CASI	X	X	X	X
Intentions to disclose	Adapted version of disclosure intentions measure for MSM (1 item) ¹⁴ .	CASI	X	X	X	X
Consequences of disclosure	Measure indicating how important each of a list of possible consequences concerning disclosure was to them when considering disclosing to a specific person ²⁹ .	CASI	X	X	X	X
Potential Moderators						
Brief Symptom Inventory (BSI)	The BSI yields nine primary symptom scales and global indices and has norms for adolescents and adults ³⁰ .	CASI	X		X	X
The Alcohol, Smoking, and Substance Involvement Screening Test (ASSIST)	Individuals respond to eight items assessing the frequency and consequences of drug and alcohol use ³¹ .	CASI	X		X	X
Other Outcomes of Interest						
Retention in Care	# missed and scheduled visits over last 6 months	CASI	X		X	X
STIs	New diagnosis of rectal/urethral gonorrhea or chlamydia or syphilis in last 6 months.	Medical Chart abstraction CASI	X		X	X
Adherence	A visual analogue scale (VAS) will be used to assess antiretroviral therapy adherence over the last 3 months ³² .	CASI	X		X	X
PrEP uptake in serodiscordant partners	Participants will be asked to report on any known PrEP use among their serodiscordant partners.	CASI	X		X	X
Feasibility/Acceptability and Cost						

Feasibility (participants)	Records on recruitment, retention (missed assessments) and follow-up attempts will be kept. Intervention usage will include: # of times participant accessed the intervention, average time spent on the site, and # of activities completed.	App Metrics		X		
Acceptability	Both a scale adapted from Horvath et al ³³ , and The System Usability Scale is a validated 10-measure scale that assesses subjective usability of a system. It is scored from 0 to 100, and a score of 68 or greater indicates that the online intervention is acceptable ^{34,35} .	CASI		X		
TT specific Acceptability	Features liked, disliked with some write in questions, avatar specific acceptability	CASI		X		
Cost	Resources used to provide standard of care visits, installation and orientation to Tough Talks, clinic visits, and any unexpected consequences of the two intervention approaches recorded as part of the feasibility data collection.	CRFs, staff tools	X	X	X	X

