6.5 Three-Month Assessment

A second assessment should occur 90 days (3 months) after study enrollment. However, the assessment may occur 15 days prior to or 30 days after the ideal three-month assessment time point. SMART will aid study staff in ensuring retention. SMART maintains participant follow-up timelines, tracks participant communications, and automates sending of e-mail, text reminders, and calendar invites to participants for follow-up survey and visit completion. At three months, all participants will complete a second online survey and staff will conduct a medical chart abstraction for VL results in the week window surrounding the three-month follow up visit (both before and after). Participants will complete the 3-month follow up survey remotely and will receive \$25 for completion. Payment is not contingent upon having a VL result in the required window. Participants who miss their 1-month follow up are eligible to complete their 3-month visit.

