9.0 MONITORING UNTOWARD EFFECTS ASSOCIATED WITH OR RESULTING FROM STUDY

Site research staff must first follow both the UNC IRB and their own IRB's procedure for reporting and managing untoward effects.

There are three types of untoward effects to be identified: 1) those related to the participant, 2) those related to the study staff, and 3) those related to the neighborhood/community (*if applicable*).

First, the study will catalogue any untoward effect related to the participant. Reporting is required for occurrences including social harms, psychological distress, and serious life-threatening events such as suicide attempts. These may be immediately apparent to the study staff, such as the participant's emotional upset state requiring referral for counseling; or they may be delayed and reported later to study staff, such as physical harm to an individual for having participated in the study. Study staff will notify the UNC/Duke teams via secure email with a subject line stating that immediate response is necessary. Study staff will be briefed with best practices and trainings on the scope of possible untoward effects and how to report events.

Second, study staff may encounter untoward events during sessions that personally affect them. Training and guidance will seek to minimize this risk. Nonetheless, an assessment of the cost of conducting this study must include cataloguing these events as well. The UNC/Duke team will be notified of these events so that they may be immediately addressed, evaluated, and then modify guidance or expanded to minimize similar risk to other study staff.

Third, a critically important area that any community-based study intends to evaluate is the impact, including untoward effects, of the project on the community. This will be done informally for this protocol with untoward events being reported to the protocol team.

All untoward effects/adverse events/unanticipated problems will also need to be reported to the UNC IRB if they meet all three of the following criteria:

"Unanticipated problems involving risks to subjects or others" (UPIRSO) refers to any incident, experience, or outcome that:

- 1) is unexpected (in terms of nature, severity, or frequency) given (a) the research procedures that are described in the protocol-related documents, such as the IRB-approved research protocol and informed consent document; and (b) the characteristics of the subject population being studied;

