In addition to the main six-month CAI outcome (any CAI with a potentially susceptible partner in the last 3 months), we will conduct a separate analysis in which “potentially susceptible partner” is defined as a partner who is not known to be HIV-positive or taking HIV medications (including PrEP). Additionally, we will compare the intervention and control arms with respect to the number of CAI acts in the last three months according to partner HIV and PrEP status (known HIV-positive, HIV-negative and not on PrEP, HIV-negative and on PrEP, unknown HIV status). Finally, linear mixed models will be fitted to all continuous outcome measures (i.e., self-regulation, self-efficacy to disclose, disclosure outcome expectations, consequences of disclosure, and intentions to disclose) to estimate the relative change in mean response from baseline to 6 months between intervention and SOC groups. Before fitting all models we will look for balance between treatment arms to assess the success of randomization, and we will adjust for possible confounding variables to improve precision and validity where needed. In the event that loss to follow-up is differential across treatment arms, we will employ inverse probability weighting to correct for this selection bias. We will test hypotheses using the likelihood ratio test, and goodness-of-fit among models will be assessed using the likelihood-ratio test, AIC and BIC criteria. Intervention completion and acceptability will be assessed at 1 month, and sensitivity analyses will evaluate how our findings for primary outcomes are influenced when we account for observed intervention completion.

Transmission Model

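### No arm is asked a standard question about harms that followed a real disclosure, so harms are likely to be under-recorded and detection may differ by arm

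*Combined protocol and SAP*

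**What the plan says.** Section 9.0 sets the duty: "Reporting is required for occurrences including social harms, psychological distress, and serious life-threatening events such as suicide attempts". It then describes two ways in which such effects come to light. The first is direct: "These may be immediately apparent to the study staff". The second is later report: "they may be delayed and reported later to study staff, such as physical harm to an individual". Sections 7.3.1 and 7.4.1 provide CRFs for untoward effects and adverse events, without restriction by arm.

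In Table 2 (Schedule of Events), the Consequences of disclosure row is described as a "Measure indicating how important each of a list of possible consequences concerning disclosure was to them when considering disclosing". The secondary analysis plan in Section 10.3.3 places it among the continuous outcomes for linear mixed models: "self-regulation, self-efficacy to disclose, disclosure outcome expectations, consequences of disclosure, and intentions to disclose". The Cost row adds staff recording of "any unexpected consequences of the two intervention approaches recorded as part of the feasibility data collection".

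On setting, Section 11.3.1 states twice: "All data collection will take place in secure and supervised clinical settings". Section 6.5 says: "Participants will complete the 3-month follow up survey remotely". Sections 5.1, 5.4.3 and 6.6 likewise make follow-up surveys online or allow them to be done remotely.

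**The concern.** The intervention prepares users for rejection and poor reactions (Table 1), and actual disclosure behaviour is itself an outcome in Table 2. The trial therefore counts disclosures without a standard question on what came of them. The foreseeable harms, such as a lost relationship, threats or being outed, happen in participants' own lives over six months, largely out of staff sight. Participants may be as young as 16 and may enrol under a waiver of parental consent (Section 4.4).

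At stake is what the trial can say about safety. Section 11.3.2 calls the balance of risk and benefit favourable. A low count gathered by passive reporting could not confirm that, because it might only mean that nobody asked. The Consequences of disclosure row adds to the problem, since its name suggests harm capture that its description does not provide.

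**Working it through.** The documents give no harm rate and no detection rate, so there is no planned figure to reproduce. The check is to list every route by which a harm could be recorded and ask what each one collects.

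| Source | Arms and times | Does it ask whether a harm followed a disclosure? |
|---|---|---|
| Consequences of disclosure (Table 2, 10.3.3) | All; baseline, 1, 3, 6 months | No; rates importance of possible consequences |
| Disclosure self-regulation (Table 2) | All; baseline, 1, 3, 6 months | No; desired and actual disclosure |
| BSI (Table 2) | All; baseline, 3, 6 months | No; general symptoms, listed as a moderator, absent at one month |
| Untoward-effect CRFs (7.3.1, 7.4.1, 9.0) | All; no schedule for asking | Records what reaches staff; no solicited question described |
| Cost row (Table 2) | Worded for the two interventions; all time points | Staff record; no participant question described |
| Exit interviews (5.4.3, 6.4) | 10-15 in each intervention arm, from one month | Open questions on perceived impact; none in SOC |
| Contact before assessments (8.1) | All | Content not stated |
| Study blood draw (6.6) | Any arm, if no eligible viral load | None described |

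No row is a systematic question about experienced harm. Section 10 plans no tabulation of harms.

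**Staff contact after enrolment.** Arm 2 alone has a staffed intervention session, in weeks 2 to 4 (Section 6.3), in person or by video. Exit interviews reach 10/66 = 15% to 15/66 = 23% of each intervention arm. The scheduled surveys are the same online instrument in all arms.

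**Undercounting (illustration; all rates assumed).** Recorded events per arm = 66 × true risk × detection. With 50% detection in every arm:
- true risk 5%: 66 × 0.05 = 3.3 true events, 1.7 recorded
- true risk 10%: 6.6 true, 3.3 recorded
- true risk 20%: 13.2 true, 6.6 recorded

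Equal detection distorts no comparison, but it still understates harm.

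**How much one early visit could skew detection (illustration; assumptions stated).** Suppose harms fall evenly over 26 weeks, the Arm 2 visit catches every harm before it, and background detection b is 20% or 40%. Exit interviews are left out, being planned in equal number in Arms 1 and 2. With f the share of harms before the visit, Arm 2 detection = f + (1 − f) × b, and the spurious ratio is that divided by b.
- f = 2/26 = 0.077: b = 0.20 gives 0.26, ratio 1.3; b = 0.40 gives 0.45, ratio 1.1
- f = 4/26 = 0.154: b = 0.20 gives 0.32, ratio 1.6; b = 0.40 gives 0.49, ratio 1.2

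Under these assumptions the ratio is 1.1 to 1.6. Harms concentrated early, or rapport that raises later reporting, would make it larger. A visit that catches less would make it smaller.

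**The case against.** A reader might infer more: that the clinic arm will look more harmful because it is watched more, that SOC has no comparable harm count, and that the comparison between arms is therefore biased. The documents do not support this.

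- The duty in Section 9.0 and the CRFs apply to participants in any arm. The Cost row names only the two interventions, but it is a costing item that also covers standard-of-care visits. Its wording does not remove SOC from harm reporting.
- Psychological distress is one of the reportable harms, and the BSI measures it in the same way in all arms at baseline, 3 and 6 months.
- Arm 2's extra session comes early. It cannot observe events in later months, when scheduled contact is nearly the same across arms.
- Section 10 plans no comparison of harms between arms, and Section 2.3 states no safety hypothesis. There is no planned harms estimate to bias.
- CRF contents and staff scripts are not reproduced, and Section 11.3.1 mentions a data and safety monitoring plan that is not set out. A solicited question could sit there.

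These points limit the claim about differential detection. They do not supply the missing question: the BSI cannot show violence, outing or a lost relationship, and it is not linked to disclosure. If a standard question exists elsewhere, Table 2 should list it. The sentence on supervised settings is a drafting conflict. It does not by itself show that harms go unrecorded.

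**Conclusion.** The point holds as a gap in ascertainment. As described, the plan has no solicited, arm-neutral measure of harms experienced after disclosure and no planned tabulation of them. Under-recording is likely. Detection may differ by arm, but its direction and size cannot be established from the documents; the ratio of 1.1 to 1.6 is only what one set of assumptions yields. Viral suppression and the other efficacy comparisons are untouched. Confidence is high on the missing question and low on differential detection. The conclusion assumes that no unreproduced form or monitoring plan already contains such a question. This should be changed, because the remedy is cheap and without it a low harm count would carry little weight as evidence of safety.

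**What to change.** 1. Add one short block of about 5-6 items, identically worded, to the existing 1-, 3- and 6-month CASI in all three arms. Ask about events since the last survey: loss of a relationship, threats or violence, disclosure by a third party, loss of housing or work, and distress. Give each a yes/no for whether it was related to disclosing one's status. Section 6.4 lets the one-month survey run up to 160 days late, so record the completion date and the period covered.
2. List the block as a row in Table 2, and reword the Cost row to cover all three arms.
3. State in Section 10 that counts from the block will be tabulated descriptively by arm, with staff-observed events shown separately.
4. Reconcile the supervised-settings sentence, in both places in Section 11.3.1, with the remote procedures in Sections 5.1, 5.4.3, 6.5 and 6.6. Reconcile the handling of online answers that signal risk with Section 8.3, which addresses risk that a participant divulges.

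The cost is slightly longer surveys, programming in Qualtrics and an IRB modification. Recorded harm counts will rise because participants are asked, and the report should say so.
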